4.2 Exclusion Criteria

Patients who meet any of the following criteria will not be eligible for the study:

1. Neutropenia defined as absolute neutrophil count <500 cells/ μ L
2. Diagnosis of deep-seated *Candida*-related infections causing intraperitoneal candidiasis, septic arthritis, osteomyelitis, endocarditis, myocarditis, meningitis, or central nervous system infection or site of infection that would require antifungal treatment to exceed maximal duration of study drug (14 days)
3. Hepatosplenic candidiasis
4. Blood culture, or any other culture, positive for *C. krusei*
5. Received >2 days (>48 hours) equivalent of prior systemic antifungal treatment at approved doses to treat the current episode of candidemia (e.g., 2 consecutive doses of an echinocandin)

Note: \leq 5 days (\leq 120 hours) equivalent of prior antifungal treatment is permitted for patients with candidemia caused by *Candida* spp. with documented resistance to the specific prior antifungal administered
6. Life expectancy of <72 hours in the opinion of the Investigator
7. Severe hepatic impairment (Child-Pugh Score >9 points) at any time during 2 weeks prior to dosing
8. Patients receiving hemodialysis
9. Known human immunodeficiency virus, active hepatitis B virus, or hepatitis C virus (HCV) infections (defined as hepatitis B surface antigen or HCV ribonucleic acid positivity)
10. Alanine aminotransferase or aspartate aminotransferase \geq 5 \times upper limit of normal (ULN)
11. Total bilirubin >3 \times ULN, unless isolated hyperbilirubinemia or due to documented Gilbert's disease
12. Female patient is pregnant or lactating
13. Inappropriate fungal infection source control (e.g., persistent indwelling catheters or intravascular devices)
14. Investigational drug administered within 30 days prior to dosing
15. Prior participation in this or any previous study of APX001
16. Concomitant use of medication that is a strong inducer of CYP enzymes (e.g., rifampin, carbamazepine, phenytoin, rifabutin, efavirenz, nevirapine, phenobarbital, modafinil, nafcillin, St. John's Wort, and enzalutamide)
17. Any other condition or laboratory abnormality that, in the opinion of the Investigator, would put the patient at unacceptable risk for participation in the study or may interfere with the assessments included in the study

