7.1.3. Baseline Definition

For microbiological data, baseline pathogen(s) are *Candida spp*. isolated from the last positive blood sample collected within 96 hours prior to the first dose of study drug.

For all efficacy and safety endpoints, baseline is defined as the last measurement or assessment prior to the first dose of study drug.

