7.5.2. Clinical Laboratory Tests

Central laboratory test results (chemistry, hematology, coagulation, and urinalysis) at each scheduled visit and change from baseline will be summarized with descriptive statistics.

Shift tables from baseline to each scheduled post-baseline visit will be provided for selected chemistry parameters (ALT, AST, ALP, Total Bilirubin, Creatinine, and Creatinine Kinase) and hematology parameters (Hematocrit, Hemoglobin, Platelets, White blood cell count and differential). For chemistry parameters, the following categories will be used: < the lower limit of normal (LLN), normal, >ULN to $\leq 2 \times ULN$, $\geq 2 \times ULN$ to $\leq 3 \times ULN$, $\geq 3 \times ULN$ to $\leq 5 \times ULN$, $\geq 5 \times ULN$, and missing. For hematology parameters, the following categories will be used: low, normal, high, and missing.

The number and percentage of patients with the following potentially clinically significant abnormal liver function tests at any post-baseline visit will be summarized:

- ALT \geq 3×ULN;
- ALT \geq 5×ULN;

- ALT $\geq 10 \times ULN;$
- AST \geq 3×ULN;
- AST \geq 5×ULN;
- AST $\geq 10 \times ULN;$
- ALT or AST \geq 3×ULN;
- Total Bilirubin >1.5×ULN;
- Total Bilirubin >2×ULN;
- ALP \geq 1.5×ULN;
- ALP $\geq 2 \times ULN$;
- ALT or AST \geq 3×ULN and Total Bilirubin >1.5×ULN;
- ALT or AST \geq 3×ULN and Total Bilirubin >2×ULN; and
- Potential Hy's Law cases: ALT or AST \ge 3×ULN and Total Bilirubin >2×ULN, and ALP \le 2×ULN

A listing of patients with any post-baseline clinically significant abnormal liver function tests will be presented.

All clinical laboratory data will be listed. Values outside the normal ranges will be flagged.

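### The liver outlier and potential Hy's Law counts ignore baseline, although eligible patients can meet 10 of the 14 criteria before the first dose

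*SAP*

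**What the plan says.** SAP 7.5.2 defines 14 liver criteria and states that the patients with these "abnormal liver function tests at any post-baseline visit will be summarized" as numbers and percentages. The last criterion, potential Hy's Law, combines ALT or AST of at least 3×ULN "and Total Bilirubin >2×ULN, and ALP" of no more than 2×ULN. None of the 14 mentions the baseline value, a rise, or a multiple of baseline. The listing of patients with clinically significant liver tests is also selected on post-baseline values.

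SAP 7.1.3 does supply a baseline: "baseline is defined as the last measurement or assessment prior to the first dose of study drug". SAP 7.5.2 uses it for change-from-baseline summaries and for shift tables: "Shift tables from baseline to each scheduled post-baseline visit will be provided for selected chemistry parameters". It also plans a listing of all laboratory data with out-of-range values flagged.

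On entry, Protocol 4.2 excludes "Alanine aminotransferase or aspartate aminotransferase" only at 5×ULN or above (no. 10). It excludes total bilirubin only above 3×ULN, and even then "unless isolated hyperbilirubinemia or due to documented" Gilbert's disease (no. 11). Hepatic impairment is excluded only when severe: "Severe hepatic impairment (Child-Pugh Score >9 points) at any time during 2 weeks prior to dosing" (no. 7). None of the 17 exclusion criteria limits ALP.

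**The concern.** A row that counts post-baseline threshold crossings is easy to interpret when patients enter below the threshold. Here many of the thresholds lie inside the permitted entry range. A patient who enters above one and stays there is counted in the same way as a patient who crosses it for the first time on treatment. Likewise, a patient stable at ALT 3.5×ULN and one who goes from 3.5× to 4.9×ULN look the same in the 3×ULN rows.

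Safety is part of the primary objective (Protocol 2.1). The study has one arm, so no concurrent comparison shows how much of a count reflects liver abnormality already present at entry. The combined rows and the Hy's Law row matter most to a reader looking for a liver signal, and they are the rows for which no other planned summary gives baseline status.

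**Working it through.** The plan gives no figure to reproduce: the sample size of about 20 was set without a formal calculation (SAP 3), and no expected rate of liver abnormality is stated.

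**Step 1: which criteria can an eligible patient meet with no change?** Inputs are the entry limits in Protocol 4.2 (ALT and AST <5×ULN, total bilirubin ≤3×ULN, ALP unrestricted) and the 14 criteria in SAP 7.5.2. The allowance for higher bilirubin is not used. Each criterion was tested with the post-baseline values equal to the entry values.

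| Criterion (×ULN) | Can be met unchanged from entry? |
|---|---|
| ALT ≥3; AST ≥3; ALT or AST ≥3 | Yes (3 rows) |
| Total bilirubin >1.5; >2 | Yes (2 rows) |
| ALP ≥1.5; ≥2 | Yes (2 rows) |
| ALT or AST ≥3 with bilirubin >1.5; with bilirubin >2 | Yes (2 rows) |
| Potential Hy's Law | Yes (1 row) |
| ALT ≥5; ALT ≥10; AST ≥5; AST ≥10 | No (4 rows) |

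That gives 3 + 2 + 2 + 2 + 1 = 10 rows that can be met, and 14 − 10 = 4 that cannot. The four hold only if the baseline value stays within the entry limits. Eligibility rests on local Screening results, whereas later samples go to the central laboratory (Protocol 8.7).

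**Step 2: one illustrative patient.** Entry and all later values: ALT 4×, AST 4×, total bilirubin 2.5×, ALP 1.4×ULN. Each value is within the entry limits. The patient meets ALT ≥3, AST ≥3, ALT or AST ≥3, bilirubin >1.5, bilirubin >2, both combined rows and potential Hy's Law: 8 of 14 rows with no change.

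**Step 3: size with 20 patients.** One patient is 1/20 = 5 percentage points. For scale only, the exact (Clopper-Pearson) 95% limits are:

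- 0/20: lower 0; upper 1 − 0.025^(1/20) = 16.8%.
- 1/20: lower 1 − 0.975^(1/20) = 0.1%; upper is the p that solves P(X ≤ 1 | 20, p) = 0.025, which is 24.9%.

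**Step 4: how likely is at least one such patient?** The documents do not give the share q of patients who enter above a given threshold and stay there. With q as an assumption, the chance is 1 − (1 − q)^20:

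| Assumed q | Expected number, 20q | Chance of at least one in 20 |
|---|---|---|
| 1% | 0.2 | 18% |
| 2% | 0.4 | 33% |
| 5% | 1 | 64% |
| 10% | 2 | 88% |
| 20% | 4 | 99% |

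The low end is more natural for the combined rows, which need two elevations together; single-analyte rows could lie higher. The documents do not settle either.

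**Step 5: do the other outputs fill the gap?** The shift tables cover ALT, AST, ALP and total bilirubin one at a time and visit by visit, with no cut at 1.5× or 10×ULN. They show movement in a single analyte. They do not join ALT/AST to bilirubin within a patient, so they cannot show whether a combined or Hy's Law criterion was already met at baseline. The full laboratory listing can, but only by reading individual records.

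**The case against.** The strongest reply is that these rows are a screen. The SAP presents them as potentially significant values and potential Hy's Law cases. It does not call them treatment-emergent or drug-related, and the period counted includes follow-up after dosing ends. Inclusive counting errs towards flagging too many patients, which is the cautious direction for safety. Change from baseline, shift tables and full listings are planned, and about 20 records can be read one by one. Protocol 8.1 makes an abnormality present at Screening an adverse event only if it worsens significantly, so the adverse event tables already allow for entry status. Exclusion no. 17 lets the investigator keep out patients whose laboratory results pose unacceptable risk. The exact intervals above are not planned for safety data.

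Most of this stands. A reader might infer that the plan misstates hepatotoxicity, or passes off entry abnormalities as drug effects. The documents do not support that, because of the row labels and the other outputs. A reader might also infer that the combined rows pair ALT/AST and bilirubin from different samples. The text does not say so: it can equally mean that all parts are met at one visit, and SAP 10 leaves programming detail to a separate document. Requiring one sample is itself debatable, since the two analytes could peak at different draws.

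Replacing the counts with emergent-only rows would also have a cost: a patient who enters meeting Hy's Law and then worsens would disappear from that row.

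What the reply does not remove is that no planned summary gives the baseline status of the combined and Hy's Law counts, and that the abnormal-patient listing is selected without regard to it.

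**Conclusion.** The point holds, as a limit of one summary table. All 14 counts ignore baseline, and 10 of them, including both combined rows and potential Hy's Law, can be met by an eligible patient whose values never change. In a single-arm study the table alone does not separate abnormalities that arose or worsened after dosing from those present at entry. Case-by-case review of the listings can.

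The size is 5 percentage points per patient at 20 patients. Whether it occurs depends on the unknown share entering above a threshold: the chance of at least one unchanged patient in a row runs from 18% to 99% for assumed shares of 1% to 20%. The result rests on the stated entry limits being applied as written and on no baseline condition being added in the separate programming specifications. No hypothesis test or decision rule is affected. The change is still worth making, because the data are already collected and the rows concerned are the ones readers will look at first.

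**What to change.** In SAP 7.5.2:

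- Keep each inclusive post-baseline count as a screening row.
- Under it, split by baseline status as defined in SAP 7.1.3: (a) newly met, among patients who did not meet the criterion at baseline; (b) already met at baseline, with whether the value rose. State what counts as a rise, and for the combined rows which analytes are compared. Show patients with no baseline value separately, so that the parts add up to the inclusive count.
- In the liver listing, show baseline ALT, AST, total bilirubin and ALP beside each potential Hy's Law case.

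If the patient in Step 2 were the only one of 20 affected, the Hy's Law row would read 1/20 overall, 0/19 newly met, and 1 already met at baseline with no rise.

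The cost is SAP wording, one table program and a few listing columns. The table grows slightly, and the newly met counts have denominators that differ from row to row. No new data and no change to eligibility or conduct are needed. A rule that ALT/AST and bilirubin come from the same sample is not part of this change; the sponsor may wish to state its choice in the programming specifications.

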7.5.3. Vital Signs

Descriptive statistics will be provided for vital sign data (systolic and diastolic blood pressure, heart rate, respiratory rate, body temperature, and oxygen saturation) presented as both actual values and changes from baseline over time.

A listing of all vital signs will be provided by patient.

7.5.4. Electrocardiograms

Descriptive statistics will be provided for 12-lead ECG interval data (Heart rate, PR, QRS, QT, and RR) and changes from baseline for each scheduled visit.

All 12-lead ECG findings will be listed by patient.

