6.4.3 End of Study Drug Treatment

The EOST occurs after completion of APX001 dosing. The following procedures will be performed at EOST:

- Record vital signs, including temperature, blood pressure, heart rate, respiratory rate, oxygen saturation, and weight
- Intravascular catheter management log
- Perform dilated fundoscopic examination (only required in those patients who had positive fundoscopic findings at Screening, or as clinically indicated)
- Perform clinical laboratory assessments (serum chemistry, hematology, coagulation, and urinalysis)
- Perform 12-lead ECG
- Perform urine pregnancy test (for females of childbearing potential only)
- Perform focused, symptom-based physical examination including a neurological examination
- Collect blood culture for *Candida* spp. and blood for *Candida* spp. testing by T2MR assay
- Collect plasma sample for PK (APX001 [prodrug] and APX001A [active moiety])
 - Optional: If body fluids are sampled as part of routine patient management (e.g., bronchoalveolar lavage, lumbar puncture, paracentesis, vitreal fluid collection, abscess drainage), within approximately 2 hours of blood sampling for PK, these samples may be stored for future analysis of APX001 and APX001A levels.
- Collect other cultures and histopathology from other sites, as clinically indicated to monitor the site(s) and extent of candidemia infection
- Perform imaging tests as clinically indicated to monitor the site(s) and extent of candidemia infection
- Collect serum sample for analysis of (1,3)- β -D-glucan
- Evaluate treatment outcome
- Record concomitant medications
- Assess adverse events

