8.10 Electrocardiograms

A 12-lead ECG will be obtained at Baseline (pre-dose), EOST, EOT, and 4 weeks after EOT, or Early Termination.

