9.2.2 Analysis of Safety

All safety analyses will be performed on the Safety Population. Safety data will be patient to clinical review and summarized by appropriate descriptive statistics. A DSMB will be assigned to monitor safety on an ongoing basis throughout the study.

Analyses will be based on adverse events, vital signs, clinical laboratory assessments, and ECGs. Safety analyses will be descriptive and will be presented in tabular format with the appropriate summary statistics.

A TEAE is defined as an adverse event started on or after the administration of study drug. The number and percentage of patients with TEAEs will be tabulated by system organ class, preferred term, and by severity and relationship to treatment. Serious adverse events and adverse events leading to discontinuation from study drug will be summarized. Listings will also be provided for SAEs and adverse events leading to discontinuation of study drug.

Descriptive statistics will be provided for clinical laboratory data for both actual values and changes from Baseline over time.

Descriptive statistics will be provided for vital sign data presented as both actual values and changes from Baseline over time.

Abnormal physical examination findings will be listed.

Descriptive statistics will be provided for ECG interval data and presented as both actual values and changes from Baseline.

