2.2. Study Design

This is a multicenter, open-label, non-comparative, single-arm study to evaluate the efficacy and safety of APX001 for the first-line treatment for candidemia including suspected or confirmed antifungal-resistant candidemia in non-neutropenic patients ≥ 18 years of age. Suspicion of antifungal-resistant candidemia is sufficient and subsequent documented resistance is not required for enrollment. The Study Drug Treatment Period will be up to a maximum of 14 days (inclusive of the loading dose [Study Day 1]). After completion of 14 days study drug therapy, if further antifungal treatment is indicated to complete treatment of candidemia in accordance with standard practice guidelines, fluconazole (unless susceptibility results warrant alternative antifungal therapy) may commence for up to a further 7 days. There will be a Follow-up Period of 4 weeks (+4 days) after EOT/EOST. The total duration of participation in the study is up to approximately 7.5 weeks (inclusive of the Screening Period [≤ 96 hours prior to Baseline]).

Patients with a yeast identified in a blood culture or a positive rapid diagnostic method are eligible to be consented and screened for the study. Patients must have at least 1 positive blood test for *Candida* species (spp.) (or yeast suspected to be *Candida*) for a diagnosis of candidemia to be considered for enrollment into the study. Patients with a positive blood culture showing yeast suspected to be *Candida* must have identification of *Candida* spp. from positive blood culture confirmed prior to dosing. Screening and Baseline procedures and the start of APX001 study drug will be initiated within 96 hours from the time that the SOC blood sample for the *Candida* spp. positive culture or rapid diagnostic test was drawn.

Patients with >2 days (>48 hours) equivalent of prior systemic antifungal treatment at approved doses to treat the current episode of candidemia within 96 hours before first dose will be excluded. However, patients with *Candida* infections proven to be resistant to the specific antifungal administered may have received ≤ 5 days (≤ 120 hours) equivalent of that prior treatment (results of susceptibility testing are required prior to enrollment).

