3. SAMPLE SIZE DETERMINATION

A sample size of approximately 20 patients will be recruited in this open-label study. No formal statistical assessment for sample size determination has been performed. This sample size is considered adequate to provide the necessary data to evaluate the efficacy and safety of APX001.

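### The ECG summary in SAP 7.5.4 uses only uncorrected QT, so any change in heart rate between the pre-dose and post-treatment ECGs is mixed into the QT change from baseline

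*SAP*

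**What the plan says.** SAP 7.5.4 limits the summary to "12-lead ECG interval data (Heart rate, PR, QRS, QT, and RR) and changes from baseline for each scheduled visit", and adds a by-patient listing of ECG findings. The bracketed list is not offered as examples. Protocol 9.2.2 is generic: "Descriptive statistics will be provided for ECG interval data and presented as both actual values and changes from Baseline". Neither document mentions a rate-corrected QT, a correction formula or QT categories, and SAP section 9 declares no departure from the protocol's analyses.

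On timing, Protocol 8.10 states: "A 12-lead ECG will be obtained at Baseline (pre-dose), EOST, EOT, and 4 weeks after EOT, or Early Termination". Protocol 6.4.3 adds: "The EOST occurs after completion of APX001 dosing". SAP 7.1.3 sets the reference point: "For all efficacy and safety endpoints, baseline is defined as the last measurement or assessment prior to the first dose of study drug". Protocol 6.4.1 places the baseline procedures before dosing on the day of the first dose, and SAP 2.2 requires dosing to start within 96 hours of the qualifying blood sample.

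SAP 2.2 describes the design: "This is a multicenter, open-label, non-comparative, single-arm study to evaluate the efficacy and safety of APX001". For liver tests, unlike ECGs, SAP 7.5.2 specifies counts of patients beyond set limits: "The number and percentage of patients with the following potentially clinically significant abnormal liver function tests at any post-baseline visit will be summarized".

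**The concern.** The QT interval depends on heart rate. A patient whose heart slows between two ECGs has a longer raw QT at the second even if rate-corrected QT is unchanged. A patient whose heart speeds up can have a real increase concealed.

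Here the baseline ECG is taken early in an acute bloodstream infection, and the scheduled comparisons come after study drug has finished. Heart rate may well differ between those times. With no concurrent control, nothing in the design subtracts a rate-driven shift.

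Safety is part of the primary objective (SAP 2.1.1), and this is the only planned summary of QT. A reader could take slower heart rate for prolongation, or miss an increase in a patient whose rate rose. If QTc were derived later from the listings, nothing in the protocol or SAP would fix the formula beforehand.

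**Working it through.** **Inputs.** The interval list comes from SAP 7.5.4, and the ECG times from Protocol 8.10 and 6.4.3. The documents state no QT figure, heart rate or QTc, so there is nothing to reproduce, and every heart rate (HR) and QTc below is an assumption.

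**Formulas.** RR = 60/HR in seconds. For a fixed QTc, the raw QT is:

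- Fridericia: QT = QTc × RR^(1/3)
- Framingham: QT = QTc − 154 × (1 − RR)
- Bazett: QT = QTc × RR^(1/2)

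**Step 1: rate falls, corrected QT constant at 420 ms.** Fridericia at 110 bpm: RR = 60/110 = 0.5455, so QT = 420 × 0.8171 = 343.2 ms. At 80 bpm: RR = 0.75, so QT = 420 × 0.9086 = 381.6 ms. The difference is +38.4 ms with no change in repolarisation. Other starting rates, each falling to 80 bpm:

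| Starting HR (bpm) | Fridericia QT at start (ms) | Change, Fridericia (ms) | Change, Framingham (ms) | Change, Bazett (ms) |
|---|---|---|---|---|
| 80 | 381.6 | 0 | 0 | 0 |
| 85 | 374.0 | +7.6 | +6.8 | +10.9 |
| 90 | 366.9 | +14.7 | +12.8 | +20.8 |
| 100 | 354.2 | +27.4 | +23.1 | +38.4 |
| 110 | 343.2 | +38.4 | +31.5 | +53.5 |

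The assumed QTc matters little. For 110 to 80 bpm, the Fridericia change is +36.6 ms at QTc 400 and +40.3 ms at QTc 440. The formula matters more: for the same fall, Bazett and Framingham differ by 53.5 − 31.5 = 22.0 ms.

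**Step 2: rate rises, true QTcF increase of 20 ms (420 to 440).** Baseline QT at 80 bpm is 381.6 ms.

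- Rate rises to 90: QT = 440 × (60/90)^(1/3) = 384.4 ms, a raw change of +2.8 ms.
- Rate rises to 95: QT = 440 × (60/95)^(1/3) = 377.5 ms, a raw change of −4.1 ms.

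The 20 ms increase nearly vanishes in the first case and changes sign in the second.

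**Step 3: QTcF when Fridericia is not the true relation (110 to 80 bpm, no real change).**

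| True relation | Raw QT change (ms) | QTcF change (ms) | Artefact reduced by |
|---|---|---|---|
| Fridericia | +38.4 | 0 | 100% |
| Framingham | +31.5 | −8.5 | 1 − 8.5/31.5 = 73% |
| Bazett | +53.5 | +20.7 | 1 − 20.7/53.5 = 61% |

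QTcF removes most of the artefact in each case, but all of it only if Fridericia holds.

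**The case against.** The strongest case is that this is a minor reporting matter whose size is assumed.

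- **Assumed heart rates.** The 110 bpm case lies outside the band that scores zero on the protocol's own APACHE II form (70–109). Within that band the Fridericia figures above are +7.6, +14.7 and +27.4 ms. This stands as a caution on size. The mixing itself follows from the plan whatever the rates are.
- **Partial safeguards.** HR and RR are summarised at the same visits, clinically significant ECG findings are reportable as adverse events (Protocol 8.1), a DSMB reviews accumulating data, and the oral Phase 1 study found no clinically significant ECG findings (Protocol 1.2). HR and RR tables would reveal a group shift in rate, but they do not give each patient's corrected change. The other safeguards do not repair the summary.
- **Unseen specifications.** SAP section 10 refers to separate programming specifications, which could define QTc. This stands in part: it cannot be said that no formula is fixed anywhere. It does not alter the SAP's stated list of summarised variables.
- **Open-label data.** Writing the formula down before database lock does not guarantee that nobody has seen the ECGs. True, but it still records one choice in advance of the final analysis.
- **Limited yield.** No routine ECG is scheduled during dosing, so timing limits what these data can show more than rate correction does. That stands, and QTcF does not cure it.
- **Outlier counts.** Adding them is a preference drawn from the liver-test section. Agreed, and the point does not depend on them.

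**Conclusion.** The concern holds. As written, the only planned QT summary combines rate change with any change in repolarisation, in a single-arm comparison of a pre-dose ECG with ECGs after dosing. The omission from the protocol and SAP is certain from their text.

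Its numerical effect is not known. Under the assumed falls to 80 bpm it runs from 0 to +38.4 ms by Fridericia, and up to +53.5 ms by Bazett. In an individual whose rate rises, a true 20 ms increase can appear as close to zero or negative. These figures rest on the chosen heart rates, on corrected QT of 400 to 440 ms, and on the three formulas shown.

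The analysis is descriptive, and no hypothesis or stopping rule in these documents uses it. The change should be made because it is cheap and makes the summary interpretable.

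**What to change.** In SAP 7.5.4, before database lock:

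1. Define QTcF = QT / RR^(1/3), with RR in seconds, calculated for each ECG from its own QT and RR.
2. Report QTcF and its change from baseline by scheduled visit as the repolarisation summary. Keep raw QT, HR and RR beside it.
3. Optionally, add counts of patients with high QTcF or a large increase, as SAP 7.5.2 does for liver tests, with cut-offs chosen by the sponsor and recorded before lock.
4. State what this leaves open: no routine ECG during dosing, no control arm, about 20 patients, an EOT ECG that may follow step-down antifungal treatment, and residual error if Fridericia does not fit.

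The cost is one derived variable and added rows in the ECG table, plus one small table if the counts are included. No new data are needed. Protocol 9.2.2 refers only to ECG intervals in general, so a SAP edit is enough. The programming specifications should carry the same definition.
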